8.2 Planned recruitment rate

Within the UK approximately 10,000 patients meeting our eligibility criteria undergo radical therapy a year and 700 patients undergo FT. Thus, the potential pool of eligible patients is large and the timeline to full accrual is based on UK estimates and would allow both CHRONOS-A and CHRONOS-B to complete recruitment within 5 years and primary outcome analysis to occur after 8 years. For the pilot stage 120 patients (60 each for CHRONOS-A and CHRONOS-B) will be recruited from approximately 6 sites over 12-months. The pilot will assess feasibility of our recruitment timelines and final recruitment rates will be based on the data from the pilot.

The recruitment rate will be assessed as part of our pilot and timelines for the main stage will be adjusted accordingly. In order to allow the majority of UK sites to be eligible for the study, we will develop a centralised process for the delivery of trial therapies/interventions. In brief, if a site does not have direct access to either FT or radiotherapy or surgery then there will be a process in place for the treatment to take place in a nearby trial site that offers that treatment.

8.3 Statistical analysis

Feasibility and pilot study

The primary analysis of the feasibility stage will estimate recruitment and randomisation rate to allocated arm. Safety in terms of Adverse Events will be analysed in terms of occurrence of adverse events in each arm.

The main study will be initiated if the minimum target recruitment rate of the feasibility study is within the lower end of the confidence interval and funding has been confirmed.

Main study

Time-to-event (progression or failure depending on which of CHRONOS-A or CHRONOS-B) data will be presented using Kaplan-Meier plots. In all time-to-event analyses, patients that have not experienced the event in question will be censored at the date last seen/known to be alive. The hazard ratio (HR) will be taken from a Cox proportional hazards model, adjusted for any stratification factors used at randomisation. Differences in time-to-event outcomes will be assessed using the log-rank c2 test and expressed using a hazard ratio (HR) with a 2-sided 95% confidence interval. If there is evidence of non-PH in the treatment

Protocol No: 19CX5006 v5.0 13th July 2022

Short Title: IP4 - CHRONOS	Protocol No: 19CX5006	Sponsor: Imperial College London	Version: 5.0 Date: 13 th July 2022
			13 July 2022

effect, the HRs are difficult to interpret and the restricted mean survival time (RMST) constructed from a flexible parametric model with time varying treatment effects will take primacy.

The assumption of proportional-hazards (PH) will be tested and appropriate methods applied to the data in the case of any violation. If there is no evidence of non-PH in the treatment effect, the HR for the adjusted Cox model takes primacy. If there is evidence of non-proportional hazards in the treatment effect, the HRs are difficult to interpret and the restricted mean survival time constructed from a flexible parametric model with time varying treatment effects will take primacy.

Planned interim and sub-group analyses: Each research comparison will have a pilot stage, one pre-planned interim analysis on PFS or FFS if the research comparison were to continue to a main stage study, and a final efficacy stage on PFS or FFS.

Planned interim analyses for education: there will be a review of recruitment into each research arm and these results as well as the qualitative outcomes will be used for submission for a research doctoral thesis of [name] supervised by the Chief Investigator of this trial. The thesis will be embargoed to public release as deemed necessary by the TSC/DMC.

CHRONOS-B: Interim monitoring and analyses: For each research comparison one formal intermediate analysis is planned, where an activity "hurdle" is determined on the intermediate primary outcome measure, FFS. Each research arm needs to pass this in order to continue recruitment. This will initially be timed according to the observed number of interim events required for a formal interim analysis (Table 2).

Table 2: Guidelines for stopping accrual and trigger for analysis

Stage	Arm Ratio	Target HR	One-sided alpha	Power	HR cut-point	Control arm events
2 Activity	1:1	0.67	0.45	95%	>0.974	~47FFS
3 Efficacy	1:1	0.67	0.025	85%	-	~120FFS
Overall	-	-	0.044	83%	-	-

For each comparison that continues recruitment into its final efficacy stage, the final analysis will be triggered by a pre-specified number of definitive primary outcome events being reported for the relevant patients on the control arm of that comparison (Table 2).

Further details of the planned analysis of the secondary outcomes and methods for dealing with missing data will be given in the Statistical Analysis Plan. Any deviation from the statistical analysis plan will be described and the reason for the deviation explained.

i. Primary Outcome Measure Analysis

The primary endpoint (PFS or FFS) analysis consists of a Cox proportional hazard model to investigate the effect of the intervention on PFS/FFS adjusted by the stratification variables.

The assumption of proportional-hazards (PH) will be tested and appropriate methods applied to the data in the case of any violation. If there is no evidence of non-PH in the treatment effect, the HR for the adjusted Cox model takes primacy. If there is evidence of non-proportional hazards in the treatment effect, the HRs are difficult to interpret and the

Short Title:	Protocol No:	Sponsor:	Version: 5.0
IP4 - CHRONOS	19CX5006	Imperial College London	Date:
			13 th July 2022

restricted mean survival time (RMST) constructed from a flexible parametric model with time varying treatment effects will take primacy.

ii. Secondary Outcome Measure Analysis

Details of the secondary endpoints analysis will be outlined in the Statistical Analysis Plan document, which will be written and signed off before any analysis will commence.

iii.Adjusted analysis

Analysis will be adjusted by the pre-specified stratification variables

iv.Safety Analysis

Safety analysis consists in tabulating the frequency of serious adverse events.

Short Title: IP4 - CHRONOS	Protocol No: 19CX5006	Sponsor: Imperial College London	Version: 5.0 Date: 13 th July 2022
			10 daily 2022

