2.4 Feasibility and Pilot Endpoints

CHRONOS-A and CHRONOS-B Pilot Outcome Measures

Primary

 Feasibility and acceptance of randomisation (rate per-month per-centre averaged) and compliance to allocated arm.

Secondary

IP4 - CHRONOS 19CX5006 Imperial College London Date: 13th July 2022	Short Title: IP4 - CHRONOS	Protocol No: 19CX5006	Sponsor: Imperial College London	
---	-------------------------------	--------------------------	-------------------------------------	--

- Patients' experience of consent and recruitment, including reasons for declining participation.
- Patients' motivation to accept randomisation to, and compliance with an intervention and understanding of each trial arm.
- Patients' experience of each arm including systemic issues, erectile dysfunction, urinary symptoms and rectal symptoms.
- Healthcare professionals' attitudes to intervention arms and trial design and whether this might impact on recruitment.
- Potential improvements to recruitment processes.
- To establish the feasibility of an economic evaluation alongside the main trial.

Feasibility will be measured based on a point-estimate of recruitment rates. Eligibility will be assessed against pre-defined eligibility criteria. The reasons for ineligibility will be recorded and compared across CHRONOS-A and CHRONOS-B. The retention/compliance rate will be defined as the number of participants completing study interventions and any follow-up imaging and biopsy. The reasons for withdrawal will be documented with a questionnaire given to individuals.

The integrated qualitative component is designed to inform the primary and secondary trial objectives in the trial recruitment and testing stages. Participant interview data highlighting trial processes in need of improvement may be used in real time to allow timely protocol amendments in order to improve recruitment and retention of participants. We will also interview healthcare professionals (physicians, nurses) responsible for recruiting patients.

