9.3. Primary End Point Analysis

The proportions of patients who opted for CHRONOS-A and CHRONOS-B will be reported.

The primary analysis of the internal pilot will calculate the mean number of patients recruited and randomised per month, per centre (including only the months in which the centre is open and recruiting). Overall recruitment and randomisation rates will also be calculated, along with their corresponding 95% confidence intervals. Recruitment rate is calculated as the number of participants recruited out of the total number approached. Randomisation rate is calculated as the number of participants randomised out of the total number recruited. Graphs displaying the recruitment and randomisation rates over time will be presented. A graph displaying the actual vs target recruitment rates will also be presented. These analyses will be conducted for CHRONOS-A and CHRONOS-B.

Compliance will be summarised using the CONSORT diagram for the internal pilot (see Section 1.1.1) which includes, the number of men who have withdrawn or been lost to follow-up (with reasons), and the number who completed each stage within each treatment arm. There will be a separate CONSORT for CHRONOS-A and CHRONOS-B.

Summary statistics for time between consent and randomisation, and randomisation and treatment will be presented by treatment arm. Summary statistics will also be presented for time between consecutive visits, by treatment arm.

For CHRONOS-B only, summary statistics will also be presented for time between randomisation and start of neoadjuvant treatment, and time between start of neoadjuvant treatment and start of focal therapy.

Treatment, for CHRONOS-A and CHRONOS-B, is recorded at Visit 2 (Treatment Visit). For focal therapy arms (CHRONOS-A (Focal arm) and CHRONOS-B) treatment is recorded by date of treatment and completed treatment details at Visit 2. For the radical arm of CHRONOS-A, treatment is recorded by date of visit 2 and completed treatment details on Radiotherapy/Brachytherapy Log and Prostatectomy Log at Visit 2. The proportions of patients in each treatment arm who underwent treatment will be presented, along with their corresponding 95% confidence intervals.

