10.8. Figures to Present

- Graph displaying recruitment rate over time (CHRONOS-A and CHRONOS-B), for patients recruited to the trial before¹ the Covid-19 pandemic
- Graph displaying recruitment rate over time (CHRONOS-A and CHRONOS-B), for patients recruited to the trial during/after² the Covid-19 pandemic
- Graph displaying actual vs target recruitment rate over time (CHRONOS-A and CHRONOS-B), for patients recruited to the trial before¹ the Covid-19 pandemic
- Graph displaying actual vs target recruitment rate over time (CHRONOS-A and CHRONOS-B), for patients recruited to the trial during/after² the Covid-19 pandemic
- Graph displaying randomisation rate over time (CHRONOS-A and CHRONOS-B), for patients recruited to the trial before¹ the Covid-19 pandemic
- Graph displaying randomisation rate over time (CHRONOS-A and CHRONOS-B), for patients recruited to the trial during/after² the Covid-19 pandemic.

¹Patients were recruited before the Covid-19 pandemic if they were recruited to the trial before 05/03/2020 (see Section 10.1)

²Patients were recruited during/after the Covid-19 pandemic if they were recruited to the trial after 05/03/2020 (see Section 10.1).

CHRONOS

11. Statistical Requirement for Early Termination of the Study

For a predicted sample size of 60 participants per trial (CHRONOS-A and CHRONOS-B), the 95% confidence interval for an estimated recruitment rate of 33% is (0.211, 0.449). Progression to the main stage will be initiated if the recruitment rate is above 21.1%.

If the recruitment rate is below 21.1%, the results of the feasibility analysis suggest that the trial is unfeasible and should be stopped. The result will be presented to the TSC, who will make the final decision, based on the evidence shown, as to whether the trial will continue to main stage. If the recruitment rate is between 21.1% and 33%, then remedial work will be implemented to improve the recruitment rate in the main stage of the trial. If the recruitment rate is greater than or equal to 33%, the trial will be deemed feasible.

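### The SAP's 21.1% progression cut-off uses the 60 men to be recruited as the denominator of a rate among men approached, so at the pilot's likely size it can part from the protocol's confidence-interval rule, which states no target

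*Protocol*

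**What the plan says.** **Protocol 8.3**, under the feasibility and pilot heading, starts the main study on condition that the "minimum target recruitment rate of the feasibility study is within the lower end of the confidence interval". Money for the main stage must also be secured. No number is given for the minimum target. The section does not say which rate is meant, what the confidence level is, or how the interval is computed.

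**Protocol 2.4**: "Feasibility will be measured based on a point-estimate of recruitment rates". SAP section 5 repeats the sentence. Neither place contains a threshold. Protocol 2.4 also states the primary pilot endpoint on a different scale: "Feasibility and acceptance of randomisation (rate per-month per-centre averaged) and compliance to allocated arm".

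**SAP 9.3** defines the rate as a proportion: "Recruitment rate is calculated as the number of participants recruited out of the total number approached". SAP 5.1 gives the same definition.

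**SAP section 11** (early termination) takes a predicted sample size of 60 participants per trial and states that "the 95% confidence interval for an estimated recruitment rate of 33% is (0.211, 0.449"). It then sets the rule: "Progression to the main stage will be initiated if the recruitment rate is above 21.1" per cent. There are three bands. At 33% or more the trial is deemed feasible. In the middle band, "If the recruitment rate is between 21.1% and 33%, then remedial work will be implemented to improve the recruitment rate in the main stage". Below 21.1% the result points to stopping, and the TSC takes the final decision.

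**Protocol 8.1.1 and SAP 6.6** give 60 per trial as the number to be recruited in the pilot, from 6 centres over 12 months. **Protocol 11.4** leaves the statistical criteria for termination to the SAP.

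**The concern.** The protocol describes a rule that depends on a confidence interval. The SAP applies a fixed cut-off to the observed rate. The cut-off was taken from a confidence interval, but one computed on a sample size that does not match the rate's own denominator. If the denominator is wrong, 21.1% is not the lower limit of anything the pilot will estimate, and the two documents need not reach the same decision.

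This rule decides whether a 1190-patient trial and a trial of 1200 to 1260 patients go ahead. Because protocol 8.3 names no target and its wording allows several readings, the choice between them could be made after the pilot data are known.

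**Working it through.** **1. Reproduce the SAP's interval.** Inputs from SAP section 11: p = 0.33, n = 60.

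Wald: p ± 1.96·√[p(1−p)/n] = 0.33 ± 1.96·√(0.33·0.67/60) = 0.33 ± 1.96·0.0607 = (0.211, 0.449).

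This matches exactly. Other methods do not: Wilson gives (0.224, 0.456), and Clopper-Pearson for 20/60 gives (0.217, 0.467). So 21.1% is the lower Wald limit around 33% with 60 in the denominator.

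**2. Put in the denominator that the SAP defines.** The rate is recruited/approached, and 60 is the planned number recruited. At 33%, approached = 60/0.33 ≈ 182.

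Wald: 0.33 ± 1.96·√(0.33·0.67/182) = 0.33 ± 1.96·0.0349 = (0.262, 0.398).

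The lower end becomes 26.2%. The 21.1% figure would be right only if 60 men were approached, which at 33% gives about 20 recruits.

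**3. Compare the rules at 182 approached.** SAP 11 continues from 39/182 (21.4%), since 38/182 is 20.9%. Protocol 8.3 gives no target, so 33% and 21.1% from SAP 11 are tried as assumptions. Ranges cover Wald, Wilson and Clopper-Pearson limits.

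| Reading of protocol 8.3 | Starts the main study from |
|---|---|
| 33% lies inside the observed 95% interval | 48–49/182 |
| Observed rate exceeds the planning limit of 26.2% | 48/182 |
| Observed lower limit reaches 21.1% | 50–51/182 |
| Observed lower limit reaches 33% | 73–74/182 |

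On all four readings, 39 to 47 out of 182 (21.4% to 25.8%) is continue under the SAP and not start under the protocol. At 47/182 the upper 95% limit is 0.322 (Wald), 0.326 (Wilson) or 0.328 (Clopper-Pearson), all below 0.33.

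A fifth reading, that 21.1% lies inside the observed interval, does pass these counts. Taken literally it also fails pilots with 51/182 (28%) or more, so it is unlikely to be intended. The first reading has a similar literal defect at rates above about 40%, and has to be taken as a floor.

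**4. How often this matters, under the assumptions of step 3** (182 approached; protocol start from 48, the first reading with Wilson or Clopper-Pearson limits). Binomial probabilities:

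| True rate | SAP continues, P(X ≥ 39) | Protocol starts, P(X ≥ 48) | Difference |
|---|---|---|---|
| 22% | 0.603 | 0.093 | 0.51 |
| 24% | 0.815 | 0.251 | 0.56 |
| 28% | 0.982 | 0.713 | 0.27 |

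**5. Repeat with 60 men approached.** SAP 11 continues from 13/60 (21.7%).
- 33% inside the observed interval: from 13/60 (Wilson, Clopper-Pearson) or 14/60 (Wald). Agreement to within one patient.
- Observed rate above the planning limit of 21.1%: from 13/60. Identical to the SAP.
- Lower limit reaches 21.1%: from 19/60 (Wilson) or 20/60 (Wald, Clopper-Pearson). So 13–18/60 conflicts under every method.
- Lower limit reaches 33%: from 27/60 or 28/60. So 13–26/60 conflicts under every method.

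**6. The other scale.** On the per-month per-centre scale of protocol 2.4, meeting the pilot target gives 60/(6·12) = 0.83, with an exact Poisson 95% interval of 0.64 to 1.07. Protocol 8.1.1 says the main trial would require 1 to 2. The same 60 recruits out of 182 approached is 33% on the SAP's scale. Protocol 8.3 does not say which of these is tested.

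**The case against.** The best defence is that there is only one rule. Protocol 11.4 hands the statistical termination criteria to the SAP, and SAP section 11 carries a matching title. It takes a planning interval around 33% and uses its lower end as the floor, which is a fair reading of the loose sentence in protocol 8.3. At n = 60 this reading reproduces the SAP exactly, and the target-inside-the-interval reading agrees to within one patient. This stands as far as it goes. It holds only if 60 men are approached, which conflicts with the SAP's definition of the rate and the planned 60 recruits. At 182 approached, the same planning-interval logic gives 26.2%.

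SAP 11 is also not a blunt go/no-go. Counts of 39 to 47 out of 182 fall in its remedial band, and the TSC decides below 21.1%. That is correct and softens the consequence. It does not remove the gap, because within the remedial band the trial continues without a required TSC decision.

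A reader might infer more: that protocol 2.4 itself sets 21.1%, or that one pilot result is plainly both go and no-go under the two documents. The text does not support either. Protocol 2.4 and SAP 5 say only that a point estimate is used, and 21.1% appears in SAP 11 alone. Since protocol 8.3 has no target, any clash requires a target and a reading to be supplied.

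**Conclusion.** The point holds in a limited form. The firm part is that the SAP's 21.1% is a confidence limit computed with the number to be recruited in place of the number approached, and that protocol 8.3 gives no target, metric or interval method against which to check it. On the SAP's own definitions the corresponding limit is about 26.2%.

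The conditional part is the disagreement in decisions: 39 to 47 out of 182, and the 51%, 56% and 27% probabilities at true rates of 22%, 24% and 28%. These rest on a 33% target, on 182 men approached, and on the target-inside-the-interval reading. With 60 approached the disagreement nearly vanishes on the two milder readings and remains on the stricter one (13–18/60 or more). The percentages illustrate the gap under those assumptions; they are not properties of the plan as written.

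This should be corrected before the pilot is analysed. It is more than missing detail, because a stated progression threshold rests on the wrong denominator.

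**What to change.** Write one rule, in the same terms, in protocol 8.3 and SAP section 11:

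- State the metric as recruited out of approached, and say how it relates to the per-month per-centre rate in protocol 2.4.
- State the 33% target in the protocol.
- Name the interval method and level.
- Compute the limit on the number actually approached, in place of the fixed 21.1%.

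One form that keeps the SAP's three bands:

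- Observed rate at or above 33%: go.
- Observed rate below 33% but upper 95% limit at or above 33%: go with remedial work.
- Upper 95% limit below 33%: refer to the TSC.

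The point-estimate sentence in protocol 2.4 and SAP 5 can stay with a cross-reference to this rule. The funding condition is unaffected.

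The cost is wording in two documents. The one real downside is a somewhat stricter boundary: with about 182 approached, observed rates of roughly 21% to 26% would go to the TSC and no longer progress automatically.

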1.3 Aims

To deliver an overarching RCT framework to efficiently evaluate novel surgical techniques in the treatment of non-metastatic prostate cancer

CHRONOS-A

Pilot: To determine if men will agree to participate in an RCT that randomly assigns them to FT alone or radical therapy (radiotherapy or prostatectomy).

Short Title: IP4 - CHRONOS	Protocol No: 19CX5006	Sponsor: Imperial College London	Version: 5.0 Date: 13 th July 2022
			-

Main: To determine if FT alone is non-inferior when compared to radical therapy (radiotherapy or surgery) in terms of progression-free survival (PFS) at 5 years in men with clinically significant non-metastatic cancer.

CHRONOS-B

Pilot: To determine if men expressing a preference for FT will agree to participate in a multiarm, multi-stage (MAMS) RCT that randomly assigns them to FT alone or FT in combination with neoadjuvant and/or adjuvant agents.

Main: To determine if FT combined with neoadjuvant and/or adjuvant agents compared to FT alone will improve overall failure-free survival (FFS), in men with clinically significant non-metastatic cancer

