8.1.2 Main study

Sample size calculations below are for the full phase II studies based on progression-free survival (PFS):

CHRONOS-A: Progression-free survival (PFS) in our population at 5-years is approximately 85-90% after radiotherapy and similar for prostatectomy. Overall survival is high and being a 10-15 year outcome it will not be used in this study. PFS is a clinically meaningful endpoint, with precedence in other studies and can be measured in the same way in both arms (time to salvage therapies). Our hypothesis is that FT is non-inferior in terms of PFS, whilst having fewer side-effects. The question is what margin of non-inferiority should be in the main study. In the CHHIP radiotherapy RCT a 20% relative change was acceptable as a non-inferiority margin comparing one form of radiotherapy to another form of radiotherapy HR 1.208; absolute difference 5%). In the PART RCT pilot (prostatectomy versus FT), a failure of 25% (PFS 75%) for surgery compared to a maximum 35% after focal (PFS 65%) was accepted by the NIHR-HTA as a non-inferior design because the functional detriment would be substantially better.

For a patients' perspective, we can look at the unpublished NCRN COMPARE study (presented at NCRI UK Annual Conference, November 2018). This was a discrete choice experiment where 544 newly diagnosed men (~30 UK centres) were asked to make choices between different treatment scenarios. Marginal Rate of Substitution (MRS) were calculated (trade-offs men are willing to make between side-effects and survival). On average men are willing to trade 0.68% of survival chance against 1% chance of improving urinary function, with PFS and sexual function MRS at 0.41% and 0.28%. Based on the above, it is reasonable to assume 85% PFS after radiotherapy with a non-inferiority margin of 5% for FT would meet clinical and patient acceptance.

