Based on an allocation ratio of 1:1 and a non-inferiority margin of 0.05 with a 0.85 PFS rate in the standard care arm (at median 5-years), power 0.80 and alpha 0.05, drop-out after randomisation of 5%, the overall required sample size is 1190 with 136 expected total number of events. Total recruitment and follow-up period will be 8 years. If recruitment rates were deemed to be high then the power could be adjusted to 0.90 and the total sample size will be 1660 with 189 expected total number of events. This will be on the advisement of the TSC. PFS for the main Stage will be defined as transition to salvage therapies or metastases or mortality related to prostate cancer.

CHRONOS-B main stages II and III: Using the latest update of –nstage-, with an allocation ratio of 1:1:1, we anticipate approximately 1200 patients are required over 5 years to observe 120 control arm failure-free survival (FFS) events within 7.6 years. This time will be dependent on observed FFS event rates and is based on an assumption of 20 patients recruited per month. This calculation gives 85% power at the efficacy stage analysis, to detect a hazard ratio (HR) of 0.67 and is based on 20% of patients having a FFS event by 3 years (30% by 5-years).

Table 1. Sample size calculations

	Short Title: IP4 - CHRONOS	Protocol No: 19CX5006	Sponsor: Imperial College London	Version: 5.0 Date: 13 th July 2022
١				10 Gary Lore

	Stage 1	Stage 2	Overall
Alpha	0.45	0.025	0.044
Power	95%	85%	83%
Critical HR (guidance for stopping early)	0.974		-
Control Arm Events	47	120	-
Accrual	20pts/m	20pts/m	20pts/m
Cumulative Patients	1003	1200	-
Time to analysis (years)	3.4	4.2	7.6

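### CHRONOS-A sets its non-inferiority margin as 5 points of 5-year PFS but analyses a hazard ratio or RMST, and states no margin or decision rule on either scale

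*Protocol*

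**What the plan says.** Protocol 1.3 asks whether focal therapy is non-inferior to radical therapy "in terms of progression-free survival (PFS) at 5 years". Protocol 8.1.2 justifies the margin on the absolute scale, concluding that "it is reasonable to assume 85% PFS after radiotherapy with a non-inferiority margin of 5% for FT" is acceptable to clinicians and patients, and sizes the trial on "a non-inferiority margin of 0.05 with a 0.85 PFS rate in the standard care arm (at median 5-years), power 0.80 and alpha 0.05". The result is 1190 patients and 136 events, or 1660 and 189 at 90% power. The same section puts control PFS "in our population at 5-years is approximately 85-90% after radiotherapy and similar for prostatectomy".

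Protocol 8.3 moves to another scale, in text shared by CHRONOS-A and CHRONOS-B. The comparison is a log-rank test and a Cox HR, adjusted for the stratification factors, with a two-sided 95% interval. "If there is no evidence of non-PH in the treatment effect, the HR for the adjusted Cox model takes primacy"; otherwise a "restricted mean survival time (RMST) constructed from a flexible parametric model" does. The subsection on the primary outcome measure repeats this.

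The only HR margin anywhere in the protocol ("HR 1.208; absolute difference 5" points) belongs to a cited radiotherapy trial. The SAP covers the feasibility stage only. Protocol 8.3 defers secondary outcomes and missing data to the SAP, but not the primary non-inferiority criterion.

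**The concern.** A non-inferiority trial needs one estimate, one margin on the same scale, and a rule saying which confidence limit must clear it. Here the margin is a difference in proportions at a fixed time, and the estimate is a ratio or a mean time depending on a diagnostic test. If PH is rejected, the protocol yields an RMST difference with nothing to compare it against. If it is not rejected, the HR needs a conversion that nobody has written down.

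The RMST branch is not remote. Biochemical failure counts as an event only after radical therapy, and a second focal session is not an event in CHRONOS-A (Protocol 2.5 and 5.9), so event timing may well differ between arms. Non-inferiority could then turn on a margin chosen after the data are seen.

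**Working it through.** **Inputs.** From Protocol 8.1.2: control 0.85, margin 0.05 (so 0.80 at the margin), control range 0.85 to 0.90, 1:1 allocation, power 0.80 or 0.90, alpha 0.05 with sidedness not stated, dropout 5%, N 1190 or 1660, events 136 or 189.

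**1. Margin as an HR, assuming PH.** HR = ln(S − 0.05) / ln(S), where S is control PFS.
- S = 0.85: ln(0.80)/ln(0.85) = 1.373
- S = 0.90: ln(0.85)/ln(0.90) = 1.543

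**2. The protocol's own event counts.** Freedman: events = (z_alpha + z_power)² × ((HR + 1)/(HR − 1))². At one-sided 0.05 the first factor is 6.183 for 80% power and 8.564 for 90%.

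| Comparison | HR | 80% power | 90% power |
|---|---|---|---|
| 0.85 vs 0.80 (the text) | 1.373 | 251 | 347 |
| 0.90 vs 0.85 | 1.543 | 136 | 189 |
| Stated | none | 136 | 189 |

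Schoenfeld for 0.85 vs 0.80 gives 247 and 341; two-sided alpha raises the counts further. Both stated totals are matched only by 0.90 vs 0.85, Freedman, one-sided 0.05. N is matched only approximately: with an average event fraction of 0.125 and 5% dropout, 136/0.125/0.95 = 1146 and 189/0.125/0.95 = 1592, about 4% below 1190 and 1660.

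**3. What each HR would permit.**
- HR 1.543 at 0.85 control: 0.85 − 0.85^1.543 = 0.072, a 7.2-point loss.
- HR 1.373 at 0.90 control: 0.90 − 0.90^1.373 = 0.035, a 3.5-point loss.

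An upper confidence limit of, say, 1.45 would pass on one reading and fail on the other.

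**4. Margin as RMST.** No horizon is stated, so 3, 5 and 8 years are my assumptions. With exponential curves through 0.85 and 0.80 at 5 years, the rates are 0.03250 and 0.04463 per year, and RMST(T) = (1 − exp(−rate × T))/rate.

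| Horizon | Control | Focal | Difference |
|---|---|---|---|
| 3 years | 2.858 y | 2.808 y | 0.6 months |
| 5 years | 4.615 y | 4.481 y | 1.6 months |
| 8 years | 7.044 y | 6.728 y | 3.8 months |

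Those curves are proportional. RMST takes primacy only when hazards are not. Keeping the 5-point deficit, the 5-year horizon and an exponential control, and letting the focal arm's Weibull shape run from 2 to 0.5, moves the difference from about −0.4 to +3.6 months. These are illustrations rather than forecasts, but they show that 5 points fixes no RMST margin.

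**5. Power on each scale.**
- HR margin 1.373 with 136 events: √136 × ln(1.373)/2 = 1.849. Power is Φ(1.849 − 1.645) = 58% at one-sided 0.05, or Φ(1.849 − 1.960) = 46% on the two-sided 95% interval.
- 5-year difference, 0.85 in both arms, 1190 × 0.95 / 2 = 565 per arm, complete 5-year data: standard error = √(2 × 0.85 × 0.15/565) = 0.02124, and 0.05/0.02124 = 2.354. Power is Φ(2.354 − 1.645) = 76%, or Φ(2.354 − 1.960) = 65%.

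**The case against.** PFS is a time-to-event endpoint, the sizing quotes event totals, and those totals reproduce on an HR scale, so an HR analysis is not foreign to the design. The margin is stated together with its control rate, so under PH one HR, 1.37, follows from the text. A reader might infer that neither estimate can ever be compared with the margin. The documents do not support that for the HR: the conversion is available, only unwritten, and it is contradicted by the event counts.

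The switch to RMST is also pre-specified rather than improvised, and another repair than the 5-year difference is legitimate. The main stage depends on funding, and a main-stage SAP may yet be written.

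All of this stands, and it limits the point. It does not supply what is missing. Pre-specifying the switch does not give the RMST branch a margin or a horizon. No document commits a later SAP to do so.

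**Conclusion.** The point holds in limited form. As written, the RMST branch cannot yield a non-inferiority conclusion, because it has neither margin nor horizon. The HR branch can, but only after a conversion the protocol omits, and its own figures imply two values: 1.37 from the text and 1.54 from the events. At 0.85 control those are losses of 5 and 7.2 points.

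The HR conversions assume PH, and the RMST figures assume the horizons and curve shapes given. That the events came from 0.90 vs 0.85 is inferred from an exact match at both power levels; the protocol does not say so. The change is worth making before the main stage starts.

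**What to change.** For CHRONOS-A, make the primary test the difference in 5-year PFS, from Kaplan-Meier or standardised from the flexible parametric model already planned, adjusted for the stratification factors. Compare its lower confidence limit (focal minus radical) with −5 points whatever the PH test shows. Report HR and RMST as supportive. CHRONOS-B can keep the HR.

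An acceptable alternative is to pre-specify one HR margin derived from 0.85 versus 0.80, plus an RMST margin with its horizon.

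The cost is more than wording. A fixed-time difference is somewhat less efficient than an HR under PH. The sidedness of alpha must be stated and power recomputed on the chosen scale: step 5 shows neither route reaches the stated 80% at 0.85 control. For the 5-year difference at 80% power, (1.645 + 0.842)² × 2 × 0.85 × 0.15/0.05² gives 631 per arm, or 1329 in total after 5% dropout; at one-sided 0.025 it is 1687. Follow-up also needs checking: Protocol 8.2 has 5 years of recruitment and analysis after 8, so late entrants would have about 3 years, while 5.9 promises at least 5.
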